## 6 Subgroup analysis

A “Laboratory confirmed infected” subgroup will be identified and certain pre-specified analyses will also be performed. Variant 2 of viral shedding will be used for this subgroup. Analyses expected for this subgroup are identified in section 11.1.

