# Assessment n may be on the morning or evening of any given day.

\* n+1, n+2 and n+3 are the scheduled assessments following assessment n and independent of study day. For example, Assessment n could be Day 2 evening and Assessment n+3 could be Day 4 morning.

- One positive detection by viral load qPCR assay, specific for the challenge virus, in which an aliquot of the same sample has also tested positive in a viral culture assay appropriate for detecting the challenge virus (i.e. cell-based infectivity assay) from Day +2 until discharge.

For qPCR and the cell-based infectivity assay, a positive detection is any positive numeric or ‘Detected’ value. A quantifiable detection value is any numeric value and will exclude ‘Detected’ and ‘Not detected’ values.

Viral shedding (variant 2)

One or both of the following definitions must be met:

- At least 2 positive detectable assessments by viral load qPCR assay specific for the challenge virus, reported within 4 consecutive scheduled assessments and from 2 independent samples from Day +2 until discharge
- One positive detection by viral load qPCR assay, specific for the challenge virus, in which an aliquot of the same sample has also tested positive in a viral culture assay appropriate for detecting the challenge virus (i.e. cell-based infectivity assay) from Day +2 until discharge.

Laboratory-confirmed virus-like-illness (variant 1)

Virus-like-illness (variant 1) is defined as the occurrence of laboratory-confirmed infection AND any of the following:

- Upper respiratory tract illness (defined below)

 Venn Life Sciences <small>Think Research</small>	Document Number or Project Identification: VH0001 / MB05-P-01-20
	Document Version: v3
Statistical Analysis Plan	

- Lower respiratory tract illness (defined below)
- Systemic illness (defined below)
- Febrile illness (defined below).

Laboratory-confirmed virus-like-illness (variant 2)

Virus-like-illness (variant 2) is defined as the occurrence of laboratory-confirmed infection AND symptoms of either of the following:

- any two different self-reported diary card symptoms ( $\geq$  Grade 1), or
- at least one Grade 2 self-reported symptom from one or more respiratory categories (URTI and LRTI symptoms defined below).

Laboratory-confirmed virus-like-illness (variant 3)

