## 5.4 Efficacy analyses

### 5.4.1 Primary efficacy analysis

#### **Objective 1:**

To estimate the margin and variance of prophylactic effect of Intravenous (IV) treatment with Palivizumab administered 1 day prior to inoculation in the RSV human challenge model in healthy

 Venn Life Sciences Think Research	Document Number or Project Identification: VH0001 / MB05-P-01-20
	Document Version: v3
Statistical Analysis Plan	

adults compared to Placebo [assessed by quantitative reverse transcriptase-polymerase chain reaction (qRT-PCR)].

Area under the viral load-time curve (VL-AUC) of RSV-A Memphis 37b as determined by **qRT-PCR** on nasal samples collected twice daily starting two days post-viral challenge (Day +2) up to the end of quarantine will be calculated (using the trapezium rule) and tabulated per treatment group. Treatment groups will be compared using t-test if assumptions are valid (Statistical Table 14.2.1.1). In case of distribution not normal, a data transformation could be used.

qRT-PCR will be also tabulated per visit/timepoint for each treatment group (Statistical Table 14.2.1.2).

Spaghetti plots and mean value over time will be used for graphical presentation of qRT-PCR, boxplot will be used for AUC presentation (Statistical Figures 14.2.1.1 to 14.2.1.3).

Individual data for qRT-PCR (included derived data) will be presented on Listing 16.2.6.1.

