Duration of virus shedding will be analysed using Kaplan-Meier method. A Kaplan-Meier plot by treatment group will be displayed showing the duration of virus shedding (with the time axis as days since first virus shedding). A table will accompany the plot and will display the Kaplan-Meier estimates of the cumulative proportion of subjects' event free at specific time points by treatment group. Subjects who did not have a confirmed undetectable measure after their peak, will be censored at their last detectable assessment. Subjects who do not have a detectable value during quarantine (including any extended quarantine period) will be excluded from the analysis (Statistical Table 14.2.4.3 & Statistical Figure 14.2.3).

Time to Peak Virus Shedding will be described by treatment group. If the peak value is seen on more than one day, the first occurrence is used. Subjects who do not have a detectable value during quarantine (including any extended quarantine period) will be excluded from the analysis. (Statistical Table 14.2.4.4).

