## Statistical Analysis Plan

### 11 Tables, Figures and Listings

#### 11.1 List of tables

		Enrolled	Evaluable	SAF	Laboratory confirmed infected subgroup
14.1 Demographics and Baseline characteristics					
14.1.1	Subject disposition	X			
14.1.2.1	Study populations	X			
14.1.2.2	Reason for exclusion from the Evaluable set	X			
14.1.2.3	Reason for exclusion from the SAF	X			
14.1.2.4	Reason for exclusion from the PK analysis set	X			
14.1.3	Study duration and premature study discontinuation			X	
14.1.4	Protocol deviations			X	
14.1.5	Demographics data		X	X	
14.1.6	Weight, Height and BMI			X	
14.1.7	Alcohol breath test			X	
14.1.8	Urine drugs of abuse			X	
14.1.9	Urine pregnancy test			X	
14.1.10	Patient Health Questionnaire (PHQ-9)			X	
14.1.11	Generalised Anxiety Disorder Questionnaire (GAD-7)			X	
14.1.12	HIV, Hepatitis A, B & C			X	
14.1.13	Thyroid function test			X	
14.1.14	Medical history			X	
14.1.15	Previous medications			X	
14.2 Efficacy					
14.2.1.1	Primary efficacy analysis - Area under the viral load-time curve (VL-AUC) of RSV-A Memphis 37b as determined by qRT-PCR on nasal samples		X		X
14.2.1.2	qRT-PCR by visit/timepoint		X		X
14.2.2.1	Area under the viral load-time curve (VL-AUC) of RSV-A Memphis 37b as determined by cell culture on nasal samples		X		X
14.2.2.2	Cell culture by visit/timepoint		X		X
14.2.3.1	Peak viral load of RSV-A Memphis 37b - qRT PCR		X		X
14.2.3.2	Peak viral load of RSV-A Memphis 37b - Cell culture		X		X
14.2.4.1	Number of days with quantifiable qRT PCR measurements in nasal samples		X		X
14.2.4.2	Number of days with quantifiable cell culture measurements in nasal samples		X		X

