## Statistical Analysis Plan

		Enrolled	Evaluable	SAF	Laboratory confirmed infected subgroup
14.2.4.3	Duration of virus shedding		X		
14.2.4.4	Time to Peak Virus Shedding		X		
14.2.5.1	Area under the total symptom score-time curve (TSS-AUC) collected daily in the participant symptom diary card		X		X
14.2.5.2	TSS by visit/timepoint		X		X
14.2.5.3	Symptoms - Qualitative description by visit/timepoint		X		
14.2.5.4	Symptoms - Quantitative description by visit/timepoint		X		
14.2.5.5	Total symptom score - MMRM		X		X
14.2.6.1	Peak symptom score		X		
14.2.6.2	Number of days with symptoms of grade 2 or more		X		X
14.2.7.1	Total weight of nasal discharge produced		X		X
14.2.7.2	Weight of nasal discharge produced by visit		X		
14.2.7.3	Number of tissues used by participants by visit		X		
14.2.8.1	Laboratory-confirmed infection (Variant 1)		X		
14.2.8.2	Laboratory-confirmed infection (Variant 2)		X		
14.2.9	Laboratory-confirmed virus-like-illness (Variant 3)		X		
14.2.10	Incidence of Illness		X		
14.2.11.1	Proportion of Subjects with Grade 2 or Worse Symptoms on Any Occasion at any time		X		
14.2.11.2	Proportion of Subjects with Grade 2 or higher Symptoms on any occasion for each day separately		X		
14.2.11.3	Proportion of Subjects with Grade 2 or higher Symptoms on two separate occasions at any time		X		
14.2.11.4	Proportion of Subjects with Grade 2 or higher Symptoms on two separate occasions for each day separately		X		
14.2.11.5	Proportion of Subjects with any symptom (grade >=1) on any occasion at any time		X		
14.2.11.6	Proportion of Subjects with any symptom (grade >=1) on any occasion for each day separately		X		
14.2.11.7	Proportion of Subjects with any symptom (grade >=1) on two separate occasions at any time		X		
14.2.11.8	Proportion of Subjects with any symptom (grade >=1) on two separate occasions for each day separately		X		
14.2.11	Highest tympanic temperature		X		
14.3 Safety					
14.3.1.1	Summary table of adverse events			X	X
14.3.1.2	TEAEs by SOC and PT			X	

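### Ten of the fourteen tested efficacy tables are repeated in the infected-only subgroup, whose membership is a post-dosing outcome; the subgroup versions should be descriptive

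*SAP*

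**What the plan says.** Protocol 9.3.1 announces a laboratory-confirmed infected subgroup and leaves its analyses to the SAP. SAP section 6 says that "certain pre-specified analyses will also be performed. Variant 2 of viral shedding will be used for this subgroup", and adds: "Analyses expected for this subgroup are identified in section 11.1".

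Variant 2 is defined in SAP 4.2.1.4. It is met by "At least 2 positive detectable assessments by viral load qPCR assay specific for the challenge virus, reported within 4 consecutive scheduled assessments", or by one qPCR-positive sample that is also positive in culture. The window runs from Day +2 to discharge. Randomisation and dosing take place on Day -1.

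In SAP 11.1 the infected-subgroup column is marked for table 14.2.1.1 ("Primary efficacy analysis - Area under the viral load-time curve (VL-AUC) of RSV-A Memphis 37b as determined by qRT-PCR on nasal samples") and for 14.2.2.1, 14.2.3.1, 14.2.3.2, 14.2.4.1, 14.2.4.2, 14.2.5.1, 14.2.5.5 ("Total symptom score - MMRM"), 14.2.6.2 and 14.2.7.1. For the primary table, SAP 5.4.1 states: "Treatment groups will be compared using t-test if assumptions are valid (Statistical Table 14.2.1.1". SAP 5.4.2 puts a between-group t-test in the other marked tables, or the MMRM in 14.2.5.5. No sentence limits the subgroup versions to description.

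For shedding duration and time to peak (tables 14.2.4.3 and 14.2.4.4), SAP 5.4.2.1 says: "Subjects who do not have a detectable value during quarantine (including any extended quarantine period) will be excluded from the analysis".

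The primary analysis is on the evaluable population (protocol 9.3, SAP 5.3).

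**The concern.** Subgroup membership is an outcome observed after treatment. Protocol 9.1 names a lower infection rate as one of the ways palivizumab is expected to act. If it does, the infected palivizumab participants are those whom prophylaxis failed to protect, while the infected placebo participants are everyone who was susceptible. Randomisation does not make these two groups alike, so a difference between them, with its p-value and CI, does not estimate the treatment effect.

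This matters more here than in most exploratory studies. Protocol 2.2 gives the study's purpose as supplying the effect size and variance for later biosimilar equivalence or non-inferiority work. An infected-only difference reported under the same table number as the primary result could be carried forward in its place, and the plan does not say which estimate feeds the margin.

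**Working it through.** **Count.** SAP 5.4 attaches a between-group test to fourteen tables: the ten listed above plus 14.2.6.1, 14.2.8.1, 14.2.8.2 and 14.2.9. The last four are not marked for the subgroup.

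**Plan's own figure.** Inputs from protocol 9.2.2: placebo mean 20.3, SD 17.8, 70% reduction, 5% two-sided, 80% power. The difference is 0.70 × 20.3 = 14.21. Then n = 2(1.960 + 0.842)² × 17.8² / 14.21² = 24.6, so 25 per group as stated. Power at 25 is 0.806 (normal) or 0.790 (t), against 0.800 stated.

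**Infected-only values.** Assumption: 20.3 and 17.8 describe all challenged placebo participants, 73.7% are infected (protocol 9.2.2), and the uninfected have VL-AUC 0.
- Mean: 20.3 / 0.737 = 27.5
- SD: √[(17.8² + 20.3²)/0.737 − 27.54²] = √(989.1 − 758.7) = 15.2
- Expected infected on placebo: 25 × 0.737 = 18.4

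**What each contrast measures.** Suppose palivizumab prevents a fraction v of infections at random and cuts load by a fraction w in those still infected. The all-challenged mean then falls by 1 − (1 − v)(1 − w). The infected-only mean falls by w alone. Prevention is invisible to the subgroup contrast.

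**Simulation.** 20,000 trials per scenario, 25 per arm, gamma loads, two-sided t-test at 0.05; infected means VL-AUC above 0. Differences are palivizumab minus placebo, so negative favours palivizumab.

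| Assumed action | All-challenged difference | All-challenged power | Infected-only difference | Infected-only p<0.05 | of which toward harm |
|---|---|---|---|---|---|
| A. v = 0.70, w = 0 | −14.2 | 87% | −0.1 | 4.7% | 3.0% |
| B. v = 0, w = 0.70 | −14.2 | 98% | −19.3 | about 100% | 0% |
| C. Equal split, v = w = 1 − √0.3 | −14.2 | 95% | −12.4 | 67% | 0% |
| D. Lowest-load half of infections prevented, w = 0 | −5.9 | 20% | +11.6 | 49% | 49% |
| E. Chance of prevention falls gradually with load, w = 0 | −7.1 | 27% | +8.3 | 26% | 26% |

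A to C all deliver the design effect. In A about 5.5 palivizumab participants are infected, and palivizumab looks numerically worse in 47.5% of trials. D and E reduce the all-challenged mean by only 29% (5.9/20.3) and 35% (7.1/20.3).

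**Check of D.** Removing the lowest half leaves 71% of the total load on half of the infected: 27.54 × 0.7105 / 0.5 = 39.1, which is 11.6 above 27.5.

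**How much load reduction undoes D and E.** In D the subgroup difference returns to zero when w = 1 − 27.5/39.1 = 30%. In E it does so when w = 1 − 27.5/35.8 = 23%.

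**A second model.** Infection is cut to 40% by sparing the less susceptible, with w = 0 and a stated correlation between susceptibility and load.
- Correlation 0: infected-only difference about 0. The all-challenged difference is 0.40 × 27.54 − 20.3 = −9.3.
- Correlation 0.5: about +4 to +5, with significant harm in 9% to 14% of trials depending on how the correlation is built. The all-challenged difference is about −7.2.
- Correlation 1: about +10 to +11, with significant harm in 42% to 45%. The all-challenged difference is about −5.
- Adding a 20% to 30% load reduction in those still infected cuts significant harm to about 6% or less.

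**The case against.** **The subgroup tests are inferred.** Section 6 does not mention p-values. SAP 5.1.2 ties between-group tests to those specified in section 5.3, and 5.3 places efficacy analysis on the evaluable population. It stands that the reading comes from combining 11.1 with 5.4. But the efficacy tests are set out in 5.4, not 5.3, so taking that cross-reference literally would remove the primary test as well. A marked table with no other instruction would naturally be produced with its test.

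**The plan has safeguards.** The subgroup is supplementary and foreseen in the protocol. Infection incidence is compared between arms in all evaluable participants (14.2.8.1 and 14.2.8.2), so a prevention effect would be visible in the same report. No passage says that a margin will come from the infected subgroup. All of this stands and limits the stakes.

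**Harm is a corner case.** A reader might infer from D and E that the subgroup will make an effective product look harmful. The documents do not support that. It needs selective sparing of low-load infections together with almost no effect on load, while protocol 9.1 also expects lower viral titres. In B and C the subgroup favours palivizumab.

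**Shedding duration and time to peak.** A reader might take these as further biased tests. They are not: SAP 5.4.2.1 plans only a Kaplan-Meier plot and table, and a description. The count of days with quantifiable qRT-PCR has no exclusion for never-detected participants, who score 0, and it is already compared in the evaluable set (14.2.4.1).

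**Conclusion.** The point holds for ten of the fourteen tested tables. Their infected-only contrasts condition on a post-dosing outcome that the hypothesis expects palivizumab to change, and nothing marks them as descriptive.

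The typical bias is attenuation. For a product with the full design effect, the chance that the subgroup test rejects runs from about 5% (all prevention) to about 100% (all load reduction). Apparent harm is possible but extreme. These sizes rest on three things the documents do not give: the split between prevention and load reduction, the relation between susceptibility and load, and whether 20.3 and 17.8 describe all challenged placebo participants.

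It would be wrong to conclude that the primary result is compromised or that every efficacy comparison is repeated. The evaluable-set primary analysis stands, and peak symptom score, infection incidence and virus-like illness are not marked for the subgroup.

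**What to change.** In SAP sections 6 and 11.1, state three things:
- The infected-subgroup tables are descriptive: group means, SDs and plots, with no between-group p-values or CIs.
- Membership is a post-randomisation outcome.
- Effect size and variance for later biosimilar margins are taken from the evaluable set.

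In SAP 5.4.2.1, add that shedding duration and time to peak are described conditional on detection, and are to be read beside the evaluable-set comparison in table 14.2.4.1. No new rank test is needed.

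This is a cheap improvement: a few sentences and no new data. What is lost is a set of subgroup p-values and CIs that do not estimate a randomised treatment effect. The descriptive subgroup means and variances remain available.

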## 7 Sequence of analysis

### 7.1 Interim analysis

An interim analysis aiming at reassessing the sample size will be performed once at least 50% of the planned number of challenged participants have been challenged and released from the quarantine unit. This analysis will be performed by the unblinded statistician. This analysis will be solely to confirm the powering assumptions (i.e. infection rate) within the Placebo group and may allow for additional participants to be included into the study, if needed to ensure the study is not underpowered. A second interim look to the placebo infection rate may be conducted when the targeted enrolment is reached, to further consider increasing the sample-size.

Infection rate is defined as the presence of “viral shedding” measured in nasal sample as defined in section 4.2.1.4. Only the first point of the definition variant 2 will be used for the interim analysis to estimate the infection rate.

As the interim look(s) will not compare the two treatment groups on the efficacy endpoints, and as the study is exploratory and statistical testing is not its primary goal, no adjustment to the type I error rate will be made.

### 7.2 Final analysis

A final analysis will be performed when all endpoint data (safety and efficacy) up to study end (Day 28) are available.

A data-Review meeting (including adjudication of deviations) will be done after Last subject last visit. Data that can unblind the subject will not be reviewed during the data-review (PK, ADA).

The database lock will be done in two steps:

- The first database lock will include all data except those that can unblind the subject and those with a late availability (Plaque assay, PK, ADA data)
- the second database lock will include the remaining data (Plaque assay, PK, ADA data).

Consequently, TFLs will be produced in two steps. One set after each database lock.

All available tertiary endpoints available at that time may also be analysed in this step. An integrated CSR containing all data will be written and made available to the sponsor and the Investigator.

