#### 6.3. Randomisation and Blinding

hVIVO assigns a unique 6 digits number to each participant in the hVIVO database. This number will be used to identify a participant up to the point of randomisation, on source documents, on all study correspondence and in the study database. In Part 2 of the study, a separate randomisation number will be allocated to the participants at randomisation and will be used for allocation of study intervention (Palivizumab or Placebo).

In Part 2, a computer-generated randomisation schedule will be generated using SAS. Once assigned, that randomisation number shall not be reassigned.

Randomisation numbers will follow a 3-digit format e.g., [001]. A copy of the randomisation code list will be sent to the unblinded pharmacist preparing the study intervention, so that study intervention/placebo can be prepared for each participant as appropriate. The randomisation number encodes the participant's assignment to receive Palivizumab or Placebo in a 1:1 ratio.

Each participant will be dispensed blinded study intervention, labelled with his/her unique randomisation number, throughout the study. With the exception of the unblinded pharmacist, the unblinded statistician preparing the randomisation code list, the unblinded Clinical Research Associate (CRA) and the Quality Assurance (QA) auditors where necessary, the Investigator and all other clinical and non-clinical staff, (including the Study Statistician, data management staff), and the participants will remain blinded to the treatment allocation until after the database has been locked and approval for study unblinding has been given.

Following database lock, on receipt of authorisation from the Sponsor, a copy of the randomisation code list will be provided to the Study Statistician to conduct study unblinding prior to analysis.

Participants who are replaced as per Section 7.4 Participant Replacement Strategy will be replaced and assigned a new, unique randomisation number equaling the randomisation number of the replaced participant, plus 100. This will ensure that the replacement participant receives the same allocated, blinded treatment as the participant who is being replaced.

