#### 5.2.2.2 Outliers

All available data points will be included in analysis, unless a clear reason is available to exclude data. All outlier data will be reviewed during the data-review meeting and decisions regarding their use in the statistical analyses will be made.

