#### **5.4.2.4 Incidence of infection & illness**

##### **a) Objective 6:**

To estimate the margin and variance of prophylactic effect of IV treatment with Palivizumab administered 1 day prior to inoculation in the RSV human challenge model in healthy adults compared to Placebo [assessed by viral shedding of RSV-A Memphis 37b in nasal samples, in terms of incidence, duration, and peak].

Incidence of laboratory-confirmed infection (variant 1) and incidence of laboratory-confirmed infection (variant 2) will be presented by treatment group and compared using chi-square test (Statistical Tables 14.2.8.1 and 14.2.8.2).

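### By-arm outputs are planned after a first lock that leaves out the plaque assay, so the code would probably be open before culture data, which feed the infection definitions, are locked

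*SAP*

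**What the plan says.** **Lock sequence.** SAP 7.2 describes a first lock of all data "except those that can unblind the subject and those with a late availability (Plaque assay, PK, ADA data", and then states that "the second database lock will include the remaining data (Plaque assay, PK, ADA data". It continues: "Consequently, TFLs will be produced in two steps. One set after each database lock".

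**Outputs are by arm.** For infection incidence, SAP 5.4.2.4 says the results "will be presented by treatment group and compared using chi-square test (Statistical Tables 14.2.8.1 and 14.2.8.2". The other efficacy comparisons in SAP 5.4 are between treatment groups too, and SAP 5.1.1 sorts listings by treatment group.

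**Blinding.** Under Protocol 6.3, site and study staff, apart from a few named unblinded roles, "will remain blinded to the treatment allocation until after the database has been locked" and unblinding has been approved. The study statistician then receives the code in order to analyse. SAP 3.3.2.5 puts the blind review of deviations ahead of lock and code break, each in the singular.

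**Infection definitions.** In SAP 4.2.1.4, viral shedding variants 1 and 2 each have two clauses, of which one or both must be met. The first uses qPCR alone. The second begins "One positive detection by viral load qPCR assay, specific for the challenge virus" and requires that the same sample also be positive in viral culture. SAP 6 defines the infected subgroup by variant 2. SAP 7.1 limits the definition to the first clause, but for the interim analysis only.

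**Data review.** SAP 5.2.2.2 says "All outlier data will be reviewed during the data-review meeting and decisions regarding their use in the statistical analyses will be made", and SAP 5.2.2.1 leaves exceptions for retests to the same meeting. SAP 7.2 describes one such meeting, after the last subject's last visit.

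**The concern.** A two-lock plan is harmless if the late data play no part in anything reported early and nobody has discretion over them once the code is open. Here neither condition is secured in writing.

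First, infection status is among the outputs that the first TFL set would naturally contain, yet it depends on an assay that is not in the first lock. SAP 4.2.1.4 says how to treat incomplete qPCR data but not how to derive infection while culture results are outstanding.

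Second, culture VL-AUC, culture peak and number of days with quantifiable culture come wholly from plaque data. If the code opens for the first TFL set, the remaining judgement calls on these endpoints can be made by people who have seen the qPCR and symptom results by arm.

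The study exists to estimate margins and variance for later biosimilar comparisons (Protocol 2.2). Infection incidence and culture AUC are among those estimates, so it should be clear that they were settled blind.

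**Working it through.** The documents give no figure for this point, so the check is mainly a comparison of sections. The one planning number used is 25 per arm, which reproduces: with a difference of 0.70 × 20.3 = 14.21 and SD 17.8, n = 2 × (1.960 + 0.842)² × 17.8² / 14.21² = 24.6, rounded up to 25.

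**1. Does the first TFL set need the code?** By-arm tables, between-group tests and listings sorted by arm cannot be made without it. Protocol 6.3 ties code release to database lock but assumes a single lock. The SAP has two and does not say which one opens the code. SAP 7.3 walls off an unblinded statistician, but in connection with the interim results. Protocol 9.5 kept other staff blinded during a separate main analysis, but SAP 8 drops that analysis and nothing equivalent is described between the two locks. Early code release is therefore the likely reading, though it is not stated.

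**2. What depends on culture?**
- Tables 14.2.8.1 and 14.2.8.2 (infection variants 1 and 2).
- Table 14.2.9 (virus-like illness variant 3).
- The infection and virus-like-illness lines of Table 14.2.10.
- The tables marked for the infected subgroup in SAP 11.1: 8 from 14.2.1.1 to 14.2.4.2, 5 from 14.2.5.1 to 14.2.7.1, and 14.3.1.1, so 8 + 5 + 1 = 14. Four of these (14.2.2.1, 14.2.2.2, 14.2.3.2, 14.2.4.2) are culture tables that need plaque data anyway, which leaves 10.
- All 13 figures in SAP 11.2, which are marked for that subgroup. Four are culture figures, which leaves 9.

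So 4 + 10 = 14 tables and 9 figures that are not themselves culture outputs use the culture clause in whole or in part.

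**3. Who can change status at the second lock?** Because one clause suffices, anyone who meets the qPCR clause is settled at the first lock. Under variant 2, only a participant with a qPCR detection that is culture-positive in the same sample, but without two detections within four consecutive assessments, can move. Under variant 1 the two results must be quantifiable, so someone with only detected, unquantifiable qPCR results and one positive culture could also move. Movement is only from uninfected to infected.

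**4. How much could it matter?** One participant is 1/25 = 4 percentage points. As an illustration on assumed counts, take placebo 18/25 (72%, near the planning rate of 73.7%) and palivizumab 11/25 on the qPCR clause. Uncorrected chi-square = N(ad − bc)² / (product of the four margins).

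| Counts (placebo v palivizumab) | Chi-square | p |
|---|---|---|
| 18/25 v 11/25 (first lock) | 50 × 175² / (25 × 25 × 29 × 21) = 4.02 | 0.045 |
| 18/25 v 12/25 (one added on palivizumab) | 50 × 150² / (25 × 25 × 30 × 20) = 3.00 | 0.083 |
| 19/25 v 11/25 (one added on placebo) | 50 × 200² / (25 × 25 × 30 × 20) = 5.33 | 0.021 |

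A single change can matter in either direction. The table shows sensitivity and does not forecast how many changes there will be.

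**5. What discretion is left for culture data?** SAP 5.2.3.2 fixes the values for detected, not detected, above-range and invalid plaque results, and SAP 4.2.1.4 fixes what counts as positive. Still open are outliers and retests (SAP 5.2.2) and the response to non-normality. For culture AUC and number of days, SAP 5.4.2.1 allows a transformation without naming it; for culture peak it names none. SAP 5.1.2 offers the Wilcoxon test as a general alternative.

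**The case against.** Several points on the other side stand.

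- **Code-break date.** No section dates the code break relative to the two locks. A reader might infer that infection status and the culture endpoints will be finalised unblinded. The documents make this likely but do not say it, and a separate programmer for the first TFL set is possible.
- **Data-review meeting.** A reader might infer that the meeting is held before plaque results exist. SAP 7.2 names only PK and ADA as withheld from it. Late availability is mentioned for the lock, so plaque data may or may not be ready for the meeting.
- **Two infection counts.** A reader might expect two conflicting counts. SAP 7.2 does not assign the infection tables to the first set, and it also says the final analysis waits for all endpoint data. Those tables may appear only once. The sentence about waiting, however, fits poorly with a TFL set that lacks culture data.
- **Direction.** Protocol 2.3.1 (Table 1) says palivizumab may interfere with culture assays. Culture-only infections are therefore less likely on palivizumab, and the 0.045 to 0.083 shift is the less likely one.
- **Limited discretion.** Infection status follows a rule. SAP 5.2.2.2 includes all data unless there is a clear reason not to. Evaluable, safety and PK set membership does not turn on plaque results.
- **Context.** The study is exploratory, with no multiplicity adjustment.

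These points narrow the concern. They do not supply the missing statements: which lock opens the code, what the first set contains, and who reviews plaque data and when.

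**Conclusion.** The concern holds as a gap in sequencing. Followed as written, SAP 7.2 would probably open the code before plaque data are locked. It leaves infection variants 1 and 2, virus-like illness variants 1 to 3 and the infected subgroup not fully derivable as defined at the first lock. It also lets outlier, retest and transformation choices for the culture endpoints follow sight of by-arm results.

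The effect on infection counts is 4 points per reclassified participant, in one direction only, for a number of participants that the documents do not allow one to estimate and that may be zero. The conclusion rests on one inference: that by-arm TFLs after the first lock mean code release at that lock.

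It would be wrong to extend the point to the main result. The primary qRT-PCR VL-AUC in the Evaluable set uses no plaque data and is not affected. This is a worthwhile and inexpensive improvement to the plan.

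**What to change.** **Preferred.** In SAP 7.2, state that the randomisation code is released only after plaque-assay data have had blinded review and been locked, and leave only PK and ADA for the second lock. This takes a few sentences of SAP text. The downside is that the first TFL set waits for the plaque assay.

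**If that wait is not acceptable:**
- Produce every table and figure that uses the culture clause or the infected subgroup only in the second TFL set, or label first-lock versions as provisional and based on the qPCR clause alone.
- Before code release, fix the outlier, retest and transformation rules for culture VL-AUC, peak and number of days.
- Have plaque data reviewed by staff who remain blinded until the second lock.

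This alternative costs a split of the output list and some staff kept blinded for longer. Neither route requires a change to the infection definitions. Either must be in place before the code is released.
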